Effects of Different Irrigation Activation Techniques on the Healing of Large Periapical Lesions: A Randomized Controlled Study Date: 01.06.2023

Study Protocol

MATERIALS AND METHODS

Local ethics committee approval was obtained from the Recep Tayyip Erdoğan University Ethical Committee (No: 2023/136). All the participants were informed about the study protocol, and written informed consent was obtained.

Sample size calculation

The G Power 3.1.9.4 (University Kiel, Germany) program was used to calculate the effect size. The effect size was calculated on the basis of the data of Verma et al. (14), who compared the success of different irrigation techniques in healing after one year. On the basis of the chi-square test data, an effect size of 0.388 was found to be sufficient for significance, and it was calculated that a total of at least 110 samples were required with a type 1 error of 0.05 and 90% power.

Patient selection

Vertucci Class I single-rooted mandibular premolars with asymptomatic apical periodontitis and a periapical index (PAI) score of 3 or higher were included in the study. Patients with systemic diseases, bone metabolism diseases and/or drugs that affect bone metabolism (steroids and bisphosphonates) were excluded from the study. Immunocompromised patients, patients with a history of radiotherapy, pregnant patients, teeth with Miller 2 or more mobility, teeth with a periodontal pocket depth of ≥5 mm, teeth with internal and external resorption, and teeth with vertical and horizontal root fractures were excluded. Out of 150 patients aged 18 years and over, a total of 18 patients who refused to participate or did not meet the inclusion criteria were excluded from the study, and 132 patients were included. Pretreatment panoramic radiographs were obtained with a Planmeca Promax 2D S2 device (Planmeca Romexis, Helsinki, Finland). The patients were positioned so that the sagittal plane was parallel to the vertical plane of the dental panoramic machine and the Frankfurt plane was parallel to the floor. The same radiographic exposure settings (66 kVp, 8 mA and 16.6 second exposure time) were used for all patients. For each tooth, the vertical, horizontal and diagonal dimensions passing through the center of the lesion were measured via ImageJ v1.52 software (National Institutes of Health, Bethesda, United States), and the largest dimension obtained was recorded as the preoperative lesion diameter (15).

Clinical Procedure

Sonic activation was performed via the Easydo Activator device (EA; Easyinsmile (Weixiaomeichi, Changsha, China). While the solution was present in the canal, the needle tip of the device was placed in the canal 2 mm behind the determined working length, and the solutions were activated at the recommended power setting.

Group 3 (PUI)

Solutions were activated via ultrasonic tips (mode:E, setting:6) (DTE, Guilin Woodpecker Co., Guilin, Guangxi, China) and an ultrasonic device (DTE S6 Led, Guilin Woodpecker Co., Guilin, Guangxi, China). An ultrasonic tip one size smaller than the master apical file was used 2 mm behind the working length without contacting the walls.

Group 4 (PIPS)

A Fotona Er:YAG laser device (LightWalker Fotona, Ljubljana, Slovenia) was used for activation. A special conical and radial fiber tip (PIPS 300/14, Fotona) was placed in the coronal part of the pulp chamber, and the irrigation solutions in the canal were activated in SSP mode (50 μ s, 0.3 W, 15 Hz and 20 mJ) with the air and water settings turned off.

Group 5 (AutoSWEEPS)

A Fotona Er:YAG laser device (SWEEPS 600, Fotona) with an 8.5 mm long and 600 μ m diameter tapered fiber tip was used for activation. The device was set to AutoSWEEPS mode with two ultrashort micropulses (25 μ s) continuously changing at 0.3 W, 20 mJ, and 15 Hz. The tip was placed in the pulp chamber, and the solution was activated with the air and water settings turned off.

In all the activation groups, 2 mL of 17% EDTA solution (SAVER, Prime Dental, Turkey) was activated for 20 s, and this process was repeated 3 times for a total of 6 mL of EDTA activation in 1 min. Then, 2 mL of saline was applied to the canals for 20 s to prevent the chemical interaction of NaOCI and EDTA. Afterward, 2 mL of 2.5% NaOCI solution (MICROVEM, Turkey) was activated for 20 s, and this procedure was repeated 3 times for a total of 6 mL of NaOCI solution activation in 1 minute.

After the final irrigation, the canals were dried with paperpoint (DiaDent, Heungdeok-gu, Korea) and obturated via the cold lateral compaction method via an ADSeal (Meta Biomed, Cheongju, South Korea) sealer and gutta-percha. The gutta-percha was cut 1 mm below the cemento-enamel junction, and coronal restoration was performed with composite resin (Llis, FGM, Joinville, Brazil). All procedures were performed by a single operator ([name]).

Healing evaluation

PAI score and lesion diameter

At the 12-month follow-up, panoramic radiographs were taken using the same settings as those used for pretreatment radiography. PAI scores of the treated teeth were recorded, and patients were classified as "healed" (PAI <3) or "unhealed" (PAI \geq 3). PAI scoring was performed by 2 endodontists, and in cases of disagreement, a consensus was reached by discussion. Additionally, the widest diameter of the lesion at the follow-up session was measured by an endodontist ([name]) The same method was used for the preoperative measurements. The researchers who conducted the PAI and lesion size evaluations were blinded to the irrigation method and preoperative measurements.

Fractal analysis

Fractal analysis (FA) was performed by an experienced oral and maxillofacial radiologist ([name]) who was blinded to the activation method and used the fractal box counting method on panoramic radiographs with ImageJ. The program was downloaded from the internet at https://imagej.nih.gov/ij/download.html. To standardize the size and location of the ROI, a parallel line forming a right angle to the apical and long axes of the tooth was placed 1 mm apical to the root apex (Figure 2). The sequence of steps followed when FD analysis was performed was as follows (Figure 3): All digital images were opened in ImageJ v. 1.52 software (National Institutes

of Health), and 30x30 pixel sections were taken from the determined regions and saved in 'tif' format. After the area of interest to be analyzed was cropped, it was saved in 8-bit format and copied. A Gaussian filter (sigma= 35 pixels) was applied to the duplicated image. The blurred image was subtracted from the original image via subtraction. A value of 128 was added to each pixel location, and 128 was set as the threshold value regardless of the initial brightness of the image. The 128 brightness threshold image was converted to binary format. An erosion and dilatation process was applied. The inverted image was skeletonized, and FD analysis was applied to the skeletonized image via the 'box-counting' function.

To assess intraobserver reliability, the lesion diameter and fractal measurements were conducted twice with 2-week intervals by the same researchers in 20% of the teeth involved in the study.

Effects of Different Irrigation Activation Techniques on the Healing of Large Periapical Lesions: A Randomized Controlled Study Date: 30.06.2024

Statistical analysis

The Jamovi 2.3.28 statistical program was used for statistical analysis. Normal distribution in the comparisons was evaluated by the Shapiro–Wilk test, Kolmogorov–Smirnov test, Anderson–Darling test and Q–Q graph. Homogeneity between variances was analyzed by Levene's test. Since sex data were categorical, the differences between the groups were analyzed via the chi-square test. Since the distribution of age between groups was found to be normal, it was analyzed by Welch's one-way ANOVA test.

Although a normal distribution was obtained in fractal analysis, Welch's one-way ANOVA test was preferred for the comparison of irrigation groups because the variances were not homogeneously distributed, and pairwise comparisons were made with the Games–Howell test. Before and after comparisons within each group, paired sample t tests were used.

Since a normal distribution could not be obtained, the Kruskal–Wallis test was preferred for the comparison of irrigation groups for lesion size, and pairwise comparisons were made with the Dwass-Steel-Critchlow-Fligner test. Before and after comparisons within each group, the Wilcoxon rank test was used. The significance level for the statistical analysis was set to p<0.05. Additionally, intraobserver reliability was evaluated for fractal and lesion size measurements via the concordance correlation coefficient (CCC).

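### No primary outcome or testing order is named, so testing fractal dimension and lesion size each at 0.05 leaves a cross-outcome false-positive rate of about 7–10%

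*SAP*

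**What the plan says.** The Protocol (Healing evaluation) measures healing in three ways at 12 months: PAI dichotomised at 3, widest lesion diameter, and fractal dimension. On the first it says "PAI scores of the treated teeth were recorded, and patients were classified as" healed or unhealed.

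The SAP (Statistical analysis) compares the arms on two of these:

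- **Fractal dimension:** Welch's ANOVA, with Games–Howell pairwise tests. The Welch "test was preferred for the comparison of irrigation groups because the variances were not homogeneously distributed".
- **Lesion size:** "the Kruskal–Wallis test was preferred for the comparison of irrigation groups for lesion size", with Dwass–Steel–Critchlow–Fligner pairwise tests.

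No test is given for PAI healed/unhealed. One threshold covers everything: "The significance level for the statistical analysis was set to p<0.05".

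The Protocol (Sample size calculation) rests on chi-square data for one-year healing success from a cited study. It states that "an effect size of 0.388 was found to be sufficient for significance" and that "it was calculated that a total of at least 110 samples were required with a type 1 error of 0.05 and 90% power".

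Neither document uses the term primary outcome, ranks the three measures or gives an order of testing.

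**The concern.** Games–Howell and Dwass–Steel–Critchlow–Fligner deal with the 15 arm pairs (6 × 5 / 2) within one outcome. Nothing acts between outcomes, so fractal dimension and lesion size each carry a full 0.05.

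Two things are at stake. First, a chance difference on either measure could be reported as an effect of irrigation technique on healing, at a rate above the nominal 5%. Second, if PAI, diameter and fractal dimension point in different directions, the plan does not say which one answers the trial's question. The outcome type on which the trial was sized is also the one with no stated analysis.

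**Working it through.** **Inputs from the documents.** Six arms (control plus Groups 1–5); 132 patients included; w = 0.388, alpha 0.05, power 90%, N = 110 (Protocol). Two between-arm omnibus tests at 0.05 (SAP).

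**Inputs assumed.** 22 per arm (132 / 6, which needs equal allocation and no loss to follow-up); 70–75% healed; a common between-outcome correlation from 0 to 0.9; and, for three outcomes only, a PAI test at 0.05.

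**Step 1: reproduce the plan's sample size.** For a chi-square test N = λ / w², where λ is the noncentrality giving 90% power at 0.05, and w² = 0.388² = 0.1505.

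| df | λ | N = λ / 0.1505 |
|---|---|---|
| 4 | 15.405 | 102.3 |
| 5 | 16.469 | 109.4, rounded up to 110 |
| 6 | 17.419 | 115.7 |

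Only df = 5 gives 110. Six arms by two classes has (6 − 1)(2 − 1) = 5 degrees of freedom, so the stated figure fits healed/unhealed across the six arms.

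**Step 2: error across outcomes if the tests are independent.** The chance of at least one false result in k tests is 1 − 0.95^k.

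- Two outcomes (the SAP as written): 1 − 0.95² = 9.75%.
- Three outcomes (if PAI is also tested at 0.05): 1 − 0.95³ = 14.26%.

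Whatever the correlation, the rate cannot exceed 2 × 0.05 = 10% and 3 × 0.05 = 15% if each test holds its nominal level.

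**Step 3: error if the outcomes are correlated.** Null trials were simulated with six arms of 22: Welch's ANOVA for one outcome, Kruskal–Wallis for the second, and a 6 × 2 chi-square for the third. All outcomes were drawn from correlated normal variables, the third cut into healed/unhealed. There were 60,000 trials per setting; the ranges cover 70% and 75% healed and include simulation error.

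| Correlation | Two outcomes | Three outcomes |
|---|---|---|
| 0 | 9.4–9.5% | 13.7–13.8% |
| 0.3 | 9.3–9.5% | 13.5–13.7% |
| 0.5 | 9.1–9.3% | 12.9–13.1% |
| 0.7 | 8.5–8.6% | 12.1% |
| 0.9 | 7.4–7.5% | 10.3–10.6% |

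At correlation 0 the rates fall slightly below Step 2 because Kruskal–Wallis and the chi-square run at about 4.7% each at this sample size. A second simulation (ordinary F test in place of Welch, 75% healed, 100,000 trials) gave 9.6% and 13.9% at correlation 0, and 7.2% and 10.3% at 0.9.

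**What is left out.** The 12 within-arm before/after tests (6 arms × 2 outcomes) and the age and sex comparisons are not between-arm outcome tests and are not counted.

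**The case against.** **The main outcome is implied.** The sample size points to one-year healing, and Step 1 confirms that it fits healed/unhealed. This stands in part: it is good evidence of intent and supplies the basis for the fix. But an implied outcome with no test in the SAP does not rank the two that are tested.

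**Correlation shrinks the inflation.** All three measures come from panoramic radiographs of the same tooth, and PAI and diameter grade the same lesion, so high correlation cannot be ruled out. This stands: at 0.9 a little under half of the two-outcome excess over 5% has gone (about 2.5 points remain of about 4.5). A single flat percentage would therefore mislead and a range is needed. The rate still exceeds 5% throughout 0 to 0.9.

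**Readings that go too far.** A reader might infer that:

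- *All three outcomes are tested at 0.05.* The SAP gives no PAI test, so the 10–14% range is conditional on one being added; only 7–10% rests on the SAP as written.
- *The trial loses the 0.05 on which it was sized.* That 0.05 belongs to one chi-square test, which keeps its own error rate however many other outcomes are tested. The Protocol never claimed to control error across outcomes.
- *The outcome to be reported was picked from the results.* The documents do not show this, nor do they say that one significant outcome is enough to claim healing. They only leave the choice open.

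**A testing order written now may be too late.** The SAP (30.06.2024) already reports distribution and variance findings for the outcomes, so data had been examined. This stands, and the fix has to allow for it.

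**Conclusion.** The concern holds as a gap in error control across outcomes. With fractal dimension and lesion size each tested at 0.05, the chance of at least one false between-arm omnibus result is about 7–10%: 9.75% if independent, about 7.5% at a correlation of 0.9. A PAI test at 0.05, which is not in the SAP, would make it about 10–14%.

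The independent figures follow from the 0.05 alone. The correlated ones depend on the assumed arm sizes, healed rate and correlations. The rates apply when no arm differs on any of the outcomes counted. That the rate exceeds 5% does not depend on where in the assumed range the correlation lies; its exact size does. The absence of a primary outcome and of a testing order is plain from the text and needs no assumption.

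**What to change.** Replace the single-threshold sentence in the SAP with a rule that does the following:

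1. **Primary outcome.** Name 12-month healed/unhealed (healed = PAI below 3), consistent with w = 0.388, 90% power and df = 5 giving 110.
2. **Its missing analysis.** A 6 × 2 chi-square omnibus test at 0.05, or an exact test if counts are small, with multiplicity-adjusted pairwise comparisons. At 22 per arm the expected unhealed count falls below 5 once more than 1 − 5/22 = 77% heal, so the criterion for the exact test should be stated.
3. **Secondary outcomes.** Test lesion diameter and fractal dimension, by their omnibus tests, in a stated fixed order at 0.05, each only while every earlier omnibus test is significant. Otherwise report them as exploratory. The sponsor chooses and states the order.
4. **Timing.** State the date on which the order was set. If outcome data had been seen by then, label the order post hoc and present both secondary outcomes as exploratory, because an order chosen after seeing results does not protect the error rate.

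Set in advance, this rule holds the error across the omnibus tests at 0.05; it does not by itself control pairwise claims pooled over outcomes.

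The cost is a short SAP revision plus the PAI analysis, with no new data. The downside is that a significant diameter or fractal result without a significant PAI result becomes exploratory.
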